2.1.2 General Exclusion Criteria

- 2.1.2.1 Patients must not have any significant medical illnesses that in the investigator's opinion cannot be adequately controlled with appropriate therapy or would compromise the patient's ability to tolerate this therapy.
- 2.1.2.2 Patients with a history of any other cancer (except non-melanoma skin cancer or carcinoma in-situ of the cervix), unless in complete remission and off of all therapy for that disease for a minimum of 3 years are ineligible.

Version Date: 07/17/2025 Page 16 of 96

2.1.2.3 Clinically significant gastrointestinal abnormalities that may increase the risk for gastrointestinal bleeding including, but not limited to:

- Active peptic ulcer disease.
- Known intraluminal metastatic lesion/s with risk of bleeding.
- Inflammatory bowel disease (e.g. ulcerative colitis, Crohn's disease), or other gastrointestinal conditions with increased risk of perforation.
- History of abdominal fistula, gastrointestinal perforation, or intra-abdominal abscess within 28 days prior to beginning study treatment.
- 2.1.2.4 Clinically significant gastrointestinal abnormalities that may affect absorption of investigational product including, but not limited to:
- Malabsorption syndrome
- Major resection of the stomach or small bowel.
- Presence of uncontrolled infection.
- Corrected QT interval (QTc) > 480 msecs using Bazett's formula Bazett's Formula:

QTc (Bazett) =
$$\frac{QT}{\sqrt{RR}}$$

- 2.1.2.5 History of any one or more of the following cardiovascular conditions within the past 6 months:
- Cardiac angioplasty or stenting
- Myocardial infarction
- Unstable angina
- Coronary artery bypass graft surgery
- Symptomatic peripheral vascular disease
- Class III or IV congestive heart failure, as defined by the New York Heart Association (NYHA), see appendix 15.7
- Poorly controlled hypertension [defined as systolic blood pressure (SBP) of \geq 140 mmHg or diastolic blood pressure (DBP) of \geq 90mmHg].
 - Note: Initiation or adjustment of antihypertensive medication(s) is permitted prior to study entry. BP must be re-assessed on two occasions that are separated by a minimum of 1 hour; on each of these occasions, the mean (of 3 readings) SBP / DBP values from each BP assessment must be $\leq 140/90$ mmHg in order for a subject to be eligible for the study.
- History of cerebrovascular accident including transient ischemic attack (TIA), pulmonary embolism or untreated deep venous thrombosis (DVT) within the past 6 months.

Note: Subjects with recent DVT who have been treated with therapeutic anticoagulating agents for at least 6 weeks are eligible.

Version Date: 07/17/2025 Page 17 of 96

2.1.2.6 Prior major surgery or trauma within 28 days and/or presence of any non-healing wound, fracture, or ulcer (procedures such as catheter placement not considered to be major).

- 2.1.2.7 Evidence of active bleeding or bleeding diathesis.
- 2.1.2.8 Known endobronchial lesions and/or lesions infiltrating major pulmonary vessels
- 2.1.2.9 Hemoptysis in excess of 2.5 mL (or one half teaspoon) within 8 weeks of first dose of study drug.
- 2.1.2.10 Any serious and/or unstable pre-existing medical, psychiatric, or other condition that could interfere with subject's safety, provision of informed consent, or compliance to study procedures.
- 2.1.2.11 Unable or unwilling to discontinue use of inducers and inhibitors of CYP450 listed in Appendix 15.4 and BCRP and PgP inducers and inhibitors for at least 14 days or five half-lives of a drug (whichever is longer) prior to the first dose of study drug and for the duration of the study. (CYP3A4 substrates can be administered, but investigators will need to be aware of possible increased or decreased effectiveness of the non-study drug and this should be recorded in concomitant medications. Dexamethasone is acceptable although listed as a CYP3A4 inducers/inhibitors as long as the dose is 16 mg/day or lesser.
- 2.1.2.12 Any ongoing toxicity from prior anti-cancer therapy that is > Grade 1 and/or that is progressing in severity, except alopecia.
- 2.1.2.13 Ongoing use of enzyme-inducing anti-epileptic agents (EIAEDs), unless 2 week washout has elapsed form last dose of EIAED.
- 2.1.2.14 Patients must not have any significant medical illnesses that in the investigator's opinion cannot be adequately controlled with appropriate therapy or would compromise the patient's ability to tolerate this therapy.
- 2.1.2.15 Patients with a known hypersensitivity to pazopanib or topotecan or to their excipients.
- 2.1.2.16 Patients on total daily dose of dexamethasone greater than 16 mg/day.
- 2.1.2.17 Patients must not have received prior therapy with topotecan, pazopanib, or related drugs such as tyrosine kinase inhibitors, VEGF inhibitors (except bevacizumab). Prior treatment with TKIs that do not impact VEGFR -1, -2, or -3, PDGFR -a, -b of cKIT could be allowed.
- 2.1.2.18 Patients must not have any disease that will obscure toxicity or dangerously alter drug metabolism.

2.2 Pretreatment Evaluation

A complete history and neurological examination (to include documentation of the patients Karnofsky Performance Status), as well as neuro-imaging confirming tumor progression shall be performed on all patients. The scan done prior to study entry documenting progression will be

Version Date: 07/17/2025 Page 18 of 96

reviewed by the patient's treating physician. The baseline scan should be performed within 14 days of registration. Patients should not be on a steroid dose higher than 16 mg/day.

Prestudy laboratory tests shall include ECG, and laboratory studies including CBC, differential, platelets, ALT, AST, bilirubin, PT, PTT, INR, TSH and T4, creatinine, urinalysis with urine protein creatine (UPC) ratio microanalysis, and serum pregnancy test for women of childbearing potential. Prestudy tests (except pregnancy test) must be obtained within 14 days of registration. UPC ratio < 1.0. Pregnancy test must be obtained within 14 days prior to starting the study drugs.

All patients should be screened for hepatitis risk factors and any past illness of hepatitis B and hepatitis C (See appendix 15.8). If patient has positive (+) response to questionnaire the Hepatitis B and C screening test should be done and recorded in the patient's chart. If liver tests are normal patient could still go on study, but the investigator would be paying close attention to the liver function test (LFT's).

2.2.1 Documentation of tumor diagnosis

Following registration, slides from the most recent pre-registration biopsy must be submitted for review15 Unstained Paraffin slides, or a paraffin tissue block, will be obtained in all study patients from original surgery or definitive surgery or the surgery closest to initiation of this clinical trial and in those patients who will be undergoing resection at time of treatment failure.

These samples should be shipped overnight mail in an appropriate container to:

[name]. Toronto General Hospital [name] [contact]

Patients will complete a baseline MD Anderson Symptom Inventory-Brain Tumor Module (MDASI-BT) (Appendix 15.5) within 14 days (+ 3 working days) after enrollment on the clinical trial. The MDASI-BT will be completed only by the patient, unless changes in vision or weakness make this difficult. If this occurs, then the caregiver or research assistant may read the questions to the patient or assist with marking the severity number or score as described by the patient. A patient caregiver may complete the questionnaires as a patient-preference proxy if the patient's deficits preclude self-report.

2.3 REGISTRATION PROCEDURES

Patients who are candidates for the study will first be evaluated for eligibility by the local investigator. All patients must be registered both locally and centrally with BTTC.

BTTC patients will be registered with the BTTC Coordinating Center. All eligibility requirements will be checked prior to registration. The status of all regulatory documents will be checked prior to registration. No patient will be entered on protocol if they do not satisfy all regulatory document and eligibility requirements.

2.3.1 Informed Consent/Authorization

Prior to protocol enrollment and initiation of treatment, subjects must sign and date an Institutional Review Board (IRB) approved consent form.

Version Date: 07/17/2025 Page 19 of 96

Registrations must be completed after the patient has signed the informed consent and has been determined to be eligible by the local investigator.

At the time of registration, the following information will be requested by the BTTC Coordinating Center:

- A copy of a completed and signed, protocol specific, Eligibility Checklist form
- One copy of the signed and dated Informed Consent/Authorization.
- Copies of all source documents to support protocol specific eligibility. Please refer to the Operations Manual for specific source documents required.

2.3.2 Registration at the NCI

Authorized staff must register an eligible candidate with NCI Central Registration Office (CRO) within 24 hours of signing consent for patients enrolling at the lead institution. A registration Eligibility Checklist from the web site (http://home.ccr.cancer.gov/intra/eligibility/welcome.htm) must be completed and faxed to [contact]. After confirmation of eligibility at Central Registration Office, CRO staff will call pharmacy to advise them of the acceptance of the patient on the protocol prior to the release of any investigational agents. Verification of Registration will be forwarded electronically via e-mail to the research team. A recorder is available during non-working hours.

2.3.3 Participating Site Registration

All patients must be registered through the NCI Central Registration Office (CRO). A protocol registration form and cover memo will be supplied by the Coordinating Center, NCI CCR and updates will be provided as needed. Subject eligibility and demographic information is required for registration. To initially register a subject, after the participant has signed consent, complete the top portion of the form and send to Coordinating Center's Research Nurse, [name]; [contact], [contact]. Once eligibility is confirmed, send the completed eligibility checklist with the attached supporting source documents to [name]. If patient is not eligible, please notify [name]. The CRO will notify you either by e-mail or fax that the protocol registration form has been received. Questions about eligibility should be directed to the Coordinating Center's Research Nurse, [name]; [contact]; [contact], [contact].

2.3.3.1 Patient Number for Participating Institutions

Once eligibility has been confirmed by the Coordinating Center, the patient from the participating institution will be registered through the Central Registration Office. A Verification of Registration will be received from the Central Registration Office with the assigned patient ID number. The patient ID number is unique to the patient and must be written on all data and correspondence for the patient and used to enter data into the C3D database. The participating site will receive the Verification of Registration via fax or email within one working day of registration.

Version Date: 07/17/2025 Page 20 of 96

2.3.4 Initiation of Therapy

Treatment may not be initiated until the participating institution receives a faxed or emailed copy of the patient's Registration Verification Letter from the Central Registration Office.

All Patients that are eligible to receive therapy must initiate treatment within 96 hours after the registration.

The BTTC Coordinating Center must be notified in writing of any exceptions to this policy.

2.3.5 Eligibility Exceptions

Eligibility Exceptions will not be granted.

2.4 DESCRIPTIVE FACTORS

Patients with recurrent GBM or GS will be enrolled into one of the following groups: (A) Glioblastoma or gliosarcoma with no prior bevacizumab exposure: (B) Glioblastoma or gliosarcoma with prior bevacizumab exposure. Accrual goals and endpoints for each group are determined separately as described in the statistical section.

There will be a total accrual of approximately 66 eligible patients to this 2-arm Phase II study (34 recurrent GBM/GS patients with no prior exposure to bevacizumab, and 32 GBM/GS patients with prior exposure to bevacizumab).

3 STUDY IMPLEMENTATION

3.1 STUDY DESIGN

This is a 2 arm phase II trial of the combination of topotecan and pazopanib in patients with recurrent GBM or GS. Patients will be enrolled into one of the following groups: (A) Glioblastoma or gliosarcoma with no prior bevacizumab exposure: (B) Glioblastoma or gliosarcoma with prior bevacizumab exposure. Topotecan and pazopanib are administered orally daily. The primary efficacy endpoint is progression free survival (PFS) at six months from patient registration for bevacizumab naïve patients and PFS at 3 months for patients with prior bevacizumab treatment.

3.2 DRUG ADMINISTRATION

Patients will be treated with the combination of topotecan and pazopanib at the following doses:

3.2.1.1 Pazopanib: Starting dose is 600 mg (3x200mg) per day to be taken orally, daily, continuous, without food at least one hour before or two hours after a meal.

Pazopanib should be taken whole with water and must not be broken or crushed.

If a dose of pazopanib is missed, it should not be taken if it is less than 12 hours until the next dose.

3.2.1.2 Topotecan: Starting dose of topotecan is 0.25 mg orally, daily, continuous.

3.3 **DOSE MODIFICATIONS:**

3.3.1 For treatment or dose modification related questions, please contact the Academic PI or the BTTC Coordinating Center's Research Nurse [name]; [contact];

Version Date: 07/17/2025 Page 21 of 96

[contact], [contact]. Topotecan length of treatment is until progression, up to one year. Drug may be held up to 3 weeks waiting from toxicities to resolve. Drug dose will not be reduced.

3.3.2 Pazopanib length of treatment is until progression, up to one year. Dose of Pazopanib may be held up to 3 weeks waiting from toxicities to resolve and reduced to 400 mg or to 200 mg daily based on side effects. Patient may be maintained on the lower dose of pazopanib during protocol if deemed to be deriving benefit from the drug.

If a patient is felt to be deriving benefit for the agent(s) and is stable at the one year time point, based on discussion with the PI and sponsor it may be possible to continue treatment at that point.

3.3.3 Patients with stable or responding disease may be retreated at the same dose (both Topotecan and Pazopanib) or at a reduced dose level (pazopanib only), depending upon the adverse events observed in the current cycle and any adverse events present on the first day of the next cycle. If multiple toxicities are seen, the dose administered in a subsequent cycle should be based on the most severe toxicity experienced in the current cycle.

Dose modifications or delays should be made based upon whether toxicities occur within a 4-week treatment cycle or at the expected start of the next treatment cycle.

3.3.4 Within Treatment Cycles:

3.3.4.1 Topotecan:

For patients who experience Grade 3 or 4 diarrhea, or other non-hematologic toxicities, the topotecan dose can be held up to 3 weeks waiting for toxicity to resolve to < Grade 2. Drug may be resumed at that time at same dose. If toxicity does not resolve in 3 weeks, patient will be taken off study. Patients with Grade 2 diarrhea may need to follow the same dose modification guidelines.

Topotecan should not be re-administered unless the neutrophil count is more than or equal to 1.5 x 10^9 /L, the platelet count is more than or equal to 75 x 10^9 /L, and the hemoglobin level is more than or equal to 9 g/dL (after transfusion if necessary).

Standard oncology practice for the management of neutropenia is either to administer topotecan with other medications (e.g. G-CSF) or to dose reduce to maintain neutrophil counts. Please refer to section 4.1 for protocol guideline regarding G-CSF administration.

3.3.4.2 Pazopanib:

For Pazopanib, two dose reductions are permitted, from 600 to 400 or 200 mg daily or from 400 to 200 mg daily. Further dose reduction is not allowed. Patients may be maintained on the lower dose of pazopanib during protocol if deemed to be deriving benefit from the drug. Doses that are reduced for pazopanib related toxicity will not be re-escalated, even if there is minimal or no toxicity with the reduced dose. Patients whose dose has been reduced for adverse events that are subsequently not felt to be related to pazopanib may have the dose re-escalated after completion of one cycle with toxicities less than or equal to grade 1.

3.3.5 Hematologic Toxicity:

Dose Modifications Based on ANC and Platelet Counts (topotecan):

Version Date: 07/17/2025 Page 22 of 96

ANC (/mL)	P	latelets (/mL)	% of Planned topotecar		
> 1500	and	> 75,000	100%		
< 750	or	< 50,000	hold*		

^{*}Topotecan should be held. Upon recovery to ANC $\geq 1,500/\text{mL}$ and platelets to >75,000/mL, the same dose level will be administered.

3.3.6 Non-hematologic Toxicity:

Dose Modifications Based on **topotecan- or pazopanib**-Related Non-Hematologic Toxicities:

NCI Grade	% of Planned Dose
0-2+	100%+
3*	hold**
4	hold***

+For symptomatic Grade 2 toxicity, the suspect drug dose may be held at the discretion of the investigator until recovery to CTC Grade 0-1, then resume at same dose for topotecan or one dose lower for pazopanib.

- **Hold suspect drug until recovery to CTC Grade 0-1 (or to within 1 grade of starting values for pre-existing laboratory abnormalities), and then resume at same dose for topotecan or one dose level lower for pazopanib.
- ***Hold suspect drug until recovery to CTC Grade 0-1 (or to within 1 grade of starting values for pre-existing laboratory abnormalities), and then resume at same dose for topotecan or two dose levels lower for pazopanib.

3.3.6.1 Management of other drug related complications:

3.3.6.1.1.1 Management of Hepatic effects:

Cases of hepatic failure (including fatalities) have been reported during the use of pazopanib. In clinical trials with pazopanib, increase in serum transaminases (ALT, AST) and bilirubin were observed. In the majority of the cases, isolated increases in ALT and AST have been reported, without concomitant elevations of alkaline phosphatase or bilirubin. The vast majority (92.5%) of all transaminase elevations of any grade occurred in the first 18 weeks.

Monitor serum liver tests before initiation of treatment with pazopanib and at least once every 4 weeks for at least the first 4 months of treatment, and as clinically indicated. Periodic monitoring should then continue after this time period.

The following guidelines are provided for patients with baseline values of total bilirubin \leq 1.5 X ULN and AST and ALT \leq 2 X ULN.

- Patients with isolated ALT elevations between 3 X ULN and 8 X ULN may be continued on pazopanib with weekly monitoring of liver function until ALT return to Grade 1 (NCI CTCAE) or baseline.
- Patients with ALT of >8 X ULN should have pazopanib interrupted until they return to Grade 1 (NCI CTCAE) or baseline. If the potential benefit for reinitiating pazopanib treatment is considered to outweigh the risk for hepatotoxicity, then reintroduce pazopanib at a reduced dose of 400 mg once daily and measure serum

^{*}Except nausea/vomiting (unless patients are on optimal antiemetic therapy).

Version Date: 07/17/2025 Page 23 of 96

liver tests weekly for 8 weeks. Following reintroduction of pazopanib, if ALT elevations >3 X ULN recur, then pazopanib should be permanently discontinued.

• If ALT elevations >3 X ULN occur concurrently with bilirubin elevations >2 X ULN pazopanib should be permanently discontinued. Patients should be monitored until return to Grade 1 (NCI CTCAE) or baseline. Pazopanib is a UGT1A1 inhibitor. Mild, indirect (unconjugated) hyperbilirubinaemia may occur in patients with Gilbert's syndrome. Patients with only a mild indirect hyperbilirubinaemia, known or suspected Gilbert's syndrome, and elevation in ALT >3 X ULN should be managed as per the recommendations outlined for isolated ALT elevations.

Concomitant use of pazopanib and simvastatin increases the risk of ALT elevations and should be undertaken with caution and close monitoring.

Beyond recommending that patients with mild hepatic impairment are treated with 800 mg pazopanib once daily (600 mg daily for this study) and reducing the initial starting dose to 200 mg per day for patients with moderate impairment, no further dose modification guidelines based on results of serum liver tests during therapy have been established for patients with preexisting hepatic impairment.

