3.3.6.2 Monitoring and management of hypertension

In clinical studies with pazopanib, events of hypertension including hypertensive crisis have occurred. Hypertension (systolic blood pressure ≥ 150 or diastolic blood pressure ≥ 100 mm Hg) occurs early in the course of treatment (39% of cases occurred by Day 9 and 88% of cases occurred in the first 18 weeks).

Blood pressure should be well controlled prior to initiating pazopanib (see 2.1.2.5)

3.3.6.2.1 BP MONITORING:

- Check BP twice weekly for the first 2 months of therapy, then weekly for 2 months, and then once per month thereafter. On days that the patient is not scheduled for clinic visits, BP can be taken at home, local Pharmacy or local Physician's office.
- BP should be taken preferably in the morning and after resting for at least 5 minutes.
- If BP is ≥140/90, then it should be repeated twice (30 and 60 minutes after the first reading). The lowest of these 3 readings will be the one considered for grading and management purposes.
- If BP measured outside the clinic visits is ≥140/90, the result should be immediately reported to the Research Nurse and/or treating physician to take appropriate action as outlined below.

BP MANAGEMENT BASED ON GRADE (CTCAE 4.02):

Hypertension- Adverse Event Grade

Grade 1 (systolic 120-139, diastolic 80-89)

Management

- no need to modify or add anti BP meds; if the patient is already taking BP meds, reinforce need for compliance.
- continue pazopanib and topotecan at same doses.
- add or increase dose of BP meds (at the discretion of

Grade 2 (systolic BP 140-159 or

Version Date: 07/17/2025

diastolic 90-99)*

Page 24 of 96

the treating physician);

- continue topotecan;
- HOLD pazopanib at the discretion of the treating physician until AE recovers to grade 0-1, then restart same dose.

Grade 3 (systolic \geq 160 or diastolic \geq 100)

- add or increase dose of BP meds (at the discretion of the treating physician);
- continue topotecan;
- HOLD pazopanib until AE recovers to grade 0-1, then restart pazopanib reducing 1 dose level.
- DISCONTINUE pazopanib;
- patient finishes trial participation.

Grade 4 (malignant hypertension; transient or permanent neurologic deficit, hypertensive crisis)

*Note: for elevated BP to be considered grade 2 or 3 the patient should be previously normotensive or should be taking BP medication/s regularly.

3.3.6.2.2 IF THE PATIENT IS NOT COMPLIANT:

- REINFORCE need for strict compliance with current BP medication/s,

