3.3.6.13 Diarrhea

Diarrhea, including severe diarrhea requiring hospitalization, has been reported during treatment with oral topotecan. The incidence of diarrhea has been reported to be greater in patients receiving oral topotecan compared to those receiving topotecan i.v. Additionally, in patients with relapsing small cell lung cancer, greater than 65 years of age, there is substantially higher risk of

Version Date: 07/17/2025 Page 26 of 96

severe diarrhea and subsequent hospitalization than in patients less than 65 years of age. Communication with patients prior to drug administration regarding diarrhea and proactive management of all signs of diarrhea is important. Physicians are advised to follow guidelines that describe the aggressive management of this event. This includes use of anti-diarrheal agents, administration of fluids and electrolytes and interruption or discontinuation of therapy with oral topotecan.

Diarrhea related to oral topotecan can occur at the same time as drug-related neutropenia and its sequelae.

3.3.6.14 At the Start of the Next Treatment Cycle:

A new course of treatment may begin when the ANC is at least 1500/mm³ and the platelet count is at least 75,000/mm³ and any other treatment-related toxicities are less than or equal to grade 1. If after a one-week delay, all treatment related toxicities are less than or equal to grade 1, then proceed with treatment at the dose level dictated by the modifications outlined above. If treatment related toxicities have not resolved to less than or equal to grade 1 after a one-week delay, then treatment will be held again, and the patient will be evaluated weekly. If treatment will be held for 2 weeks for treatment related toxicities, then reduce the pazopanib dose by one dose level beyond that indicated by whether or not the patient had DLT in the prior cycle. If retreatment must be held for more than 2 weeks the investigator should be notified. If a patient develops another DLT at the reduced dose or if they experience a life-threatening toxicity at any time, they will be removed from study.

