- ^m Patient will be followed for overall survival when possible
- ⁿ If positive (+) response to Hepatitis questionnaire Hepatitis B and C screening test should be done.

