3.7 CRITERIA FOR REMOVAL FROM PROTOCOL THERAPY AND OFF STUDY CRITERIA

- 3.7.1 Criteria for Removal from Protocol Therapy
 - 3.7.1.1 After administration of 12 28-day cycles of treatment, unless further treatment is felt to be in the best interest of the patient by the treating physician.
 - 3.7.1.2 Progression of disease (as defined in Section **6.4.1**).

Patients must be followed by the same type of brain scan, as was used for baseline tumor measurements, and will be removed from study if progression is documented after any cycle of treatment. Patients with stable disease, partial or complete response will continue on therapy.

- 3.7.1.3 Unacceptable toxicity (see Section 3.3).
- 3.7.1.4 The patient may withdraw from the study at any time for any reason.
- 3.7.1.5 Medical or psychiatric illness which in the investigator's judgment renders the patient incapable of further therapy.
- 3.7.1.6 Treatment delay due to toxicity greater than 21 days measured from the start of the preceding cycle.
- 3.7.1.7 All reasons for discontinuation of treatment must be documented in the flow sheets

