3.7.2 Off Study Criteria

All patients will be followed for overall survival, when possible.

Patients who discontinue treatment due to progression will be followed for survival every 3 months.

Patients who come off therapy for reasons other than progression should be followed until progression or institution of new anti-tumor therapy. They should then be followed for survival.

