4 CONCOMITANT MEDICATIONS/MEASURES

4.1 G-CSF ADMINISTRATION

4.1.1.1 If neutrophil count < 1500/mm³ or platelet count < 75,000/mm³, hold topotecan until counts resolve to < grade 2 CTC grade toxicity. If neutrophil count remains < 1500/mm³ x 1 week or more, granulocyte colony stimulating factor may be used to support. If neutrophil count achieves level > 1500/mm³, patient may resume treatment with oral topotecan. If toxicities do not resolve to < CTC grade 2 after 3 weeks of drug hold, and with G-CSF support patient must be removed from study. Platelet counts that do not resolve to < CTC grade 2 after 3 weeks require removal of patient from study.

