6.1.2 Database Entry Timeframes

The following data should be entered into C3D within the specified timeframes. Source documentation will be kept at the participating site.

Treatment (Cycle) Data (To include treatment, response, AE, and clinical evaluation information)	Within 40 days after the first day of each treatment cycle.
Off Treatment Data	Within 10 days after the last date of any modality of protocol treatment.
Follow-up (Survival) Data	Within 52 days after the last treatment date and then every 90 days until Off Study (unless otherwise specified by the protocol).
Non-Treatment Data (May include Quality of Life questionnaires (MDASI-BT), Specimen Tracking information, Pathology Specimen Submission, etc.)	Within 10 days after each scheduled assessment, event, or activity.
Off Study Data	Within 10 days after the date the patient is removed from the study.

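### Treatment-exit rules take patients off study while the follow-up rules keep them on, so overall-survival data could be lost selectively

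*Combined protocol and SAP*

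**What the plan says.** Section 3.7.1 lists reasons for ending protocol therapy, among them progression and unacceptable toxicity. The rules that apply at treatment exit nevertheless speak of the study:

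- 3.3.4.1, topotecan toxicity that persists: "If toxicity does not resolve in 3 weeks, patient will be taken off study".
- 3.3.6.2, grade 4 hypertension: "patient finishes trial participation".
- 3.3.6.14, another DLT at the reduced dose, or a life-threatening toxicity: "they will be removed from study".
- 4.1.1.1, no recovery after three weeks of hold with G-CSF support: "patient must be removed from study". Platelets have a matching rule.
- 3.7.1.2, under the heading on removal from therapy: patients "will be removed from study if progression is documented after any cycle of treatment".
- 4.3.1.2, a permanent anticonvulsant change with no non-enzyme-inducing alternative: also removal from the study.

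The data rules use the same status. Section 6.1.2 wants Off Study data within 10 days of removal from the study and has survival entered "every 90 days until Off Study", with an exception where the protocol specifies otherwise. Section 3.7.3 requires an off-study form when a subject is taken off study.

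Sections 3.4.4 and 3.7.2 point the other way. All patients are followed for survival when possible, and progressors every 3 months. "Patients who come off therapy for reasons other than progression should be followed until progression or institution of new anti-tumor therapy"; after that they are followed for survival. Section 3.7.2 is headed Off Study Criteria but names no event that takes a patient off study. In the Section 3.6 calendar the F/U column has only footnote m: "Patient will be followed for overall survival when possible".

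**The concern.** A site coordinator handling a toxicity exit reads the rule for that toxicity, sees that the patient leaves the study, files the form in 3.7.3 and stops survival entry under 6.1.2. Another site, starting from 3.7.2, keeps following a similar patient. The documents do not say which text prevails.

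Overall survival is a secondary endpoint for both groups, and Section 9 estimates it, and time to progression, by Kaplan-Meier without a censoring rule. Kaplan-Meier assumes that censored patients have the same later hazard as those still observed. Patients closed out under these rules would be those with severe toxicity or documented progression, whose outlook may well be worse. If so, the curves would be too favourable.

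**Working it through.** **1. What each exit could affect.**

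| Exit | Simon count | Time to progression | Overall survival |
|---|---|---|---|
| Toxicity | Not inflated: Section 9 counts it as treatment failure, also when assessing the 6-month PFS rate | Could be censored at exit | Could be censored at exit |
| Progression | It is the event | It is the event, so no censoring | Could be censored at exit |

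The exposed analyses are therefore overall survival, for both kinds of exit, and the time-to-progression curve, for toxicity exits only.

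**2. Can both sets of rules be followed?** Not literally. If progression puts a patient off study and survival entry ends there, the 3-monthly survival follow-up of progressors in 3.4.4 and 3.7.2 never operates. If 3.7.2 prevails, the exit wording is wrong.

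**3. Illustrative size for overall survival, toxicity exits only.** The plan gives no overall-survival target and no toxicity-exit rate, so it has no figure to reproduce.

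Inputs:
- Median survival 35 weeks: Section 1.2.2, single-agent pazopanib, used here as a stand-in.
- Assumed: a fraction f = 10%, 20% or 30% exits, at a time U uniform over weeks 4 to 12; the death hazard after exit is k = 1, 1.5 or 2 times the hazard before; nothing is recorded after exit.

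Formulas:
- Weekly hazard λ = ln 2 / 35 = 0.0198.
- Kaplan-Meier with censoring at exit: S₀ = exp(−26λ) = exp(−0.515) = 0.598.
- 26-week survival of exiters if followed: M(k) = E[exp(−λU − kλ(26 − U))].
- Survival with full follow-up: (1 − f)S₀ + f·M(k). Overstatement: f·(S₀ − M(k)).

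With the numbers put in, M(1) = 0.598, M(1.5) = 0.500 and M(2) = 0.419. The gaps S₀ − M are 0, 0.097 and 0.179.

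| Exits | k = 1 | k = 1.5 | k = 2 |
|---|---|---|---|
| 10% | 0 | 1.0 points | 1.8 points |
| 20% | 0 | 1.9 points | 3.6 points |
| 30% | 0 | 2.9 points | 5.4 points |

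**4. Progressors.** If they too were closed out at removal, deaths after progression would go unrecorded. The documents give no basis for sizing this, but it would be the larger threat to overall survival, because deaths in this disease usually follow progression.

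**The case against.** The strongest reply is that the documents, read as a whole, already settle the matter. Section 3.7.1 classes progression and unacceptable toxicity (by reference to Section 3.3) as removal from therapy. Sections 6.1 and 6.1.2 keep Off Treatment, Survival and Off Study data apart. The exception in 6.1.2 lets 3.4.4 and 3.7.2 override the Off Study cut-off, and if every exit were Off Study the survival row would be almost empty. This stands as the better reading, so one cannot say that survival data run only until Off Study. It does not remove the conflict. The exception clause does not choose between two instructions that are both in the protocol, 3.7.1.2 itself mixes the two terms, and 3.7.2 defines no off-study event to correct them.

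A reader might also infer that the primary result is biased upward. The documents do not support that: a progression exit is the PFS event, and Section 9 makes toxicity dropouts failures, which can only lower the count.

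The magnitude is open to challenge, and rightly. Exit rates, exit times and hazard ratios are assumed. Section 1.2.1 puts survival after bevacizumab failure at about 10 weeks, so 35 weeks does not describe Group B. Twenty-six-week survival is not a protocol endpoint. Sampling error is also larger than the bias: with 34 patients the standard error is √(0.598 × 0.402 / 34) = 8.4 points, or about ±16.5 points at 95%.

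Finally, the anticonvulsant exit in 4.3.1.2 is neither toxicity nor progression. It belongs here because it has the same wording and falls under the same follow-up rule for exits without progression.

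**Conclusion.** The contradiction is real and should be reconciled. Applied literally, the exit rules end follow-up that 3.4.4 and 3.7.2 require, and do so in patients whose prognosis is likely to differ. At risk are Kaplan-Meier overall survival and, for toxicity exits only, time to progression; the go/no-go count is not inflated by toxicity exits. No size follows from the documents. Under the stated assumptions the overstatement of 26-week survival from toxicity exits is about 0 to 5 points, and it is zero if the hazard does not change at exit. It arises only to the extent that sites follow the exit wording rather than 3.7.2.

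**What to change.** Reconcile the sections by wording alone:

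- In 3.3.4.1, 3.3.6.2, 3.3.6.14, 3.7.1.2, 4.1.1.1 and 4.3.1.2, say that the patient is off protocol therapy. The conditions for stopping treatment stay as written.
- In 3.7.2, define off study as death, withdrawal of consent to follow-up, or loss to follow-up. The form in 3.7.3 then applies only to these.
- In 6.1.2, collect survival until one of those events.
- In the 3.6 calendar, show in the F/U column the progression follow-up that 3.7.2 already requires for patients who stop without progression.

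The cost is one wording amendment. It adds no follow-up beyond what 3.4.4 and 3.7.2 already require.
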